### 1.3.4. Efficacy in Human Epilepsy

Several preliminary studies of CBD report reductions in seizure activity for a significant subset of subjects.

Plant-derived CBD was examined as an adjunctive therapy in 15 subjects with secondary generalized epilepsy with temporal focus who were refractory to conventional treatment. The eight subjects randomized to the active arm received 200 to 300 mg/day of CBD or placebo for up to 4.5 months in addition to previously established antiepileptic drugs (AEDs). Subjects tolerated CBD well, with no signs of toxicity or serious side-effects. Four of the eight subjects receiving CBD remained almost free of convulsive crises throughout the study and three others experienced partial improvement. The clinical condition of seven subjects receiving placebo remained unchanged and one subject improved.

Parents of children with treatment-resistant epilepsy have sought CBD-enriched cannabis for treatment. In a survey, these parents reported dosages of CBD ranging from <0.5 to 28.6 mg/kg/day, as per results from medical cannabis testing facilities. Sixteen (84%) of the 19 parents eligible to respond to the survey reported a reduction in their child's seizure frequency while taking CBD-enriched cannabis. Of these, 2 (11%) reported complete seizure-freedom, 8 (42%) reported >80% reduction in seizure frequency, and 6 (32%) reported a 25% to 60% seizure reduction. Reported side-effects included fatigue and somnolence.

Realm Oil is an extract from a strain of cannabis known as Charlotte's Web and contains a CBD: $\Delta^9$ -THC ratio >20:1. Gedde and Maa reported on a small group of pediatric subjects diagnosed with various types of epilepsy who took Realm Oil for  $\geq$ 3 months. Baseline seizure frequency for these subjects ranged from 5 to 2800 events per week. Eight (8, 73%) of these subjects reported a 95% to 100% reduction in seizure occurrence, 1 (9%) reported 75% reduction, and 2 (18%) reported 20% to 45% reduction.

### 1.4. Childhood Absence Epilepsy

Although there are currently two drugs approved for childhood absence epilepsy (CAE), valproate and ethosuximide, neither are ideal. Valproate has potentially serious side effects, including weight gain, polycystic ovary disease, liver failure, and significant teratogenic effects. Ethosuximide does not control general tonic-clonic seizures that can co-exist with CAE. In a recent study comparing ethosuximide, valproic acid, and lamotrigine, freedom from failure rates where treatment failure was defined as persistence of absence seizures at Week 16 or 20, a generalized tonic-clonic seizure at any time, excessive drug-related systemic toxicity, dose-limiting toxicity after a single downward dose modification, or withdrawal initiated by the parent

or physician, was 53% (ethosuximide), 58% (valproic acid), and 29% (lamotrigine). Therefore, there is still an unmet need for more effective anti-epileptic drugs with less side effects for these seizures. As CBD has been demonstrated to be effective in the treatment of cortical mediated epileptic encephalopathies, Insys is proposing a multiple-site, open-label, dose-finding proof of concept study of Cannabidiol Oral Solution for the treatment of refractory childhood absence epilepsy.

### **1.5. Dose Selection Rationale**

Patients will initiate this long-term safety study on the final dose of Cannabidiol Oral Solution administered during the Phase 2 Study INS011-17-103.

Patients will not increase their assigned dose until the Data Monitoring Committee has approved the higher dose level in INS011-17-103. Doses of CBD may be adjusted at the investigator's discretion up to a maximum of 40 mg/kg/day.

## 1.6. Summary of Potential Risks and Benefits

As reviewed in [Section 1.2](#) and [Section 1.3](#), numerous nonclinical and clinical studies have examined other formulations of CBD. Several areas of potential concern have been identified with the use of CBD, especially in nonclinical studies. These include:

- Competitive binding of CYP proteins (thus, an impact on drug metabolism in the liver). Cannabidiol is metabolized predominantly by CYP3A4 and CYP 2C19. Cannabidiol may inhibit these 2 isozymes, as well as having small effects on CYP3A5, CYP1A1, and CYP2C9.
- Potential downregulation of immune responses involving the T, B, T-helper, and T cytotoxic subsets of leukocytes and/or those dependent on IL-2 or IFN- $\gamma$ .

Based on recent studies of cannabinoid administration in humans, controlled CBD may be safe in humans and animals. However, further studies are needed to clarify these reported in vitro and in vivo side-effects.

The inclusion/exclusion criteria, concomitant medication guidelines, and safety monitoring (AEs, clinical laboratory, vital signs, ECG, and physical examination assessments) planned for this study are intended to minimize these potential safety risks.

Criteria for removal of patients from the study will dictate discontinuation of patient participation should a safety issue arise (see [Section 3.3](#)).

Two facets of the current treatment landscape for pediatric patients with treatment-resistant absence seizures support the potential benefit for patients in this study. First, pediatric patients with treatment-resistant absence seizures continue to experience a significant unmet medical need despite ongoing treatment with currently available medications and procedures. Patients included in this study may potentially benefit from treatment with Cannabidiol Oral Solution. Devinsky et al. recently noted that pediatric patients with treatment-resistant seizures are particularly good candidates for CBD intervention. Data reviewed in [Section 1.2.2](#) and [Section 1.3.4](#) demonstrate that CBD has shown preliminary efficacy in treating epilepsy in several early-stage nonclinical and clinical studies, respectively. This study is expected to serve as a critical step in the development of Cannabidiol Oral Solution as a treatment for refractory childhood absence epilepsy.

Second, synthetic pharmaceutical grade Cannabidiol Oral Solution is expected to have several distinct advantages over cannabis plant-derived extracts:

- Availability of the drug substance does not depend on cannabis plant production. As such, the development of Cannabidiol Oral Solution will not support growth and distribution of plants from which marijuana is derived.
- Manufacture of Cannabidiol Oral Solution does not involve an extraction process whereby the derived constituents could also include a significant amount of  $\Delta^9$ -THC. The manufacturing process can be controlled so that mass quantities can be produced that are uniform in quality, purity, and consistency and can be delivered in known and predetermined quantities.
- Variability in concentration and constituents should be reduced among batches, which may improve safety and tolerability.

- Reduced concern for contamination by  $\Delta^9$ -THC, herbicides, pesticides, etc.

Approved

**2. STUDY OBJECTIVE**

The objective of this study is to assess the long-term safety and tolerability of Cannabidiol Oral Solution (CBD) in pediatric patients with treatment-resistant Childhood Absence Seizures.

Approved

### 3. INVESTIGATIONAL PLAN

#### 3.1. Overall Study Design

This is a multicenter, open-label, flexible dose study designed to assess the long-term safety and tolerability of CBD in doses ranging from 20 mg/kg/day to 40 mg/kg/day in patients with treatment-resistant childhood absence seizures. Patients must have completed INS011-17-103 to be eligible.

The Investigator will ensure that the patients legal representative [parent(s)/caregiver(s)] will receive a copy of the informed consent form for review and provide full informed consent prior to study participation.

Patients should enroll in Long-Term Safety Study (INS011-17-113) after completing Study INS011-17-103 Visit 6 (End of Study) to avoid interruption of the investigational product. Patients will have up to 2 weeks to enroll in INS011-17-113. The first visit (Visit 1) for INS011-17-113 will be after the completion of Visit 6 of INS011-17-103.

Patients will continue to receive CBD treatment for approximately 48 weeks. Patients will remain on their assigned dose or may be titrated up to a higher dose level if the Data Monitoring Committee has approved the higher dose level in INS011-17-103. **If any participant does not enroll within the 2 week window, the patient will not be eligible to enroll into the study.**

The study will consist of a Safety Period (48±2 weeks), Taper Period (10±3 days), and a Follow-up Period (30±5 days). Treatment visits will be scheduled monthly for the first 3 months and then quarterly over the remaining 9 months. All patients will complete a Visit 7 (End of Study) or Early Withdrawal Visit regardless of when they stop treatment/complete the study. A Follow-Up telephone call (Visit 9) will occur 30 days after the end of either the End of Study (Visit 7) or Early Withdrawal.

In this study, all patients will be dosed as follows:

- Once the informed consent for INS011-17-113 is provided within the required time frame, initially the patient will receive the same dose as was administered during INS011-17-103. If tolerability issues occurred during INS011-17-103, the dose can be decreased if the dose was greater than 20 mg/kg/day. If the patient received 20 mg/kg/day and the physician wants to decrease the dose, the patient should be discontinued.
- Physicians will not increase a patient's assigned dose until the Data Monitoring Committee has deemed that the higher dose is safe in INS011-17-103. Doses of CBD may be adjusted at the investigator's discretion up to a maximum of 40 mg/kg/day.
- Treatment with established antiepileptic drugs (AEDs) and therapeutic treatments (e.g., vagus nerve stimulation [VNS]) may be initiated/continued/adjusted and changes will be permitted as necessary based on safety concerns or changes in seizure control. Any changes must be documented in the eCRF.

Patients will be dosed approximately every 12 hours with food to help ensure consistent plasma levels are achieved. Patients will be dosed for 48 weeks during which the investigator will assess safety and tolerability.

The study will be terminated upon one of the following:

- The investigational product is successfully approved for marketing in the US.
- Sponsor elects to terminate INS011-17-113.
- The patient has received 48 weeks of treatment.

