#### Follow-Up Period

A Follow-up telephone call will occur 30 days after discontinuation of the study drug to assess AEs, AEDs, and record concomitant medications.

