**Table 1: Schedule of Events**

ASSESSMENTS	SAFETY PERIOD				Early Withdrawal	TAPER PERIOD	FOLLOW-UP PERIOD i	
	Visit Number	1 a	2, 3, 4 (monthly)	5, 6 (quarterly)				
Study Time Points	Day 1	Weeks 4, 8, 12		Weeks 24, 36	End of Active Treatment (Week 48)		0-10 Days	30 Days After EOS
Visit Window (Days)	± 5	± 5		± 5	± 3			± 5
Informed consent **								
Review of inclusion/exclusion criteria **								
C-SSRS					X	X		
Review of AEDs	X	X	X		X	X		X
Review Concomitant Medications	X	X	X		X	X		X
Vital Signs b	X	X	X		X	X		
Clinical Labs c	X	X	X		X	X		
12-lead ECG	X	X	X		X	X		
Urinalysis	X	X	X		X	X		
Urine pregnancy screen for post-menarchal females	X				X	X		
Physical Examination d	X	X	X		X	X		
Brief neurological Examination e	X	X	X		X	X		
Dosing with Cannabidiol Oral Solution f	X	X	X		X f	X g		
Drug Accountability	X	X	X		X	X		X
AEs	X	X	X		X	X		X

ASSESSMENTS	SAFETY PERIOD					TAPER PERIOD	FOLLOW-UP PERIOD i
Visit Number	1 a	2, 3, 4 (monthly)	5, 6 (quarterly)	7 (End of Study)	Early Withdrawal	8	9 (Phone Call)
Study Time Points	Day 1	Weeks 4, 8, 12	Weeks 24, 36	End of Active Treatment (Week 48)		0-10 Days	30 Days After EOS
Visit Window (Days)	± 5	± 5	± 5	± 3			± 5
End of Study				X	X h		

\*\* To be completed prior to enrollment into LTS, specifically within the 2 week period that is allotted post completion of Visit 6 (End of Study) of INS011-17-103.

a For patients who enroll within the first 2 weeks after completion of Visit 6 (End of Study) of INS011-17-103 protocol.

b Vital signs will be taken after a 5-minute seated rest.

c If the total bilirubin laboratory value is abnormal, direct bilirubin will be drawn.

d The physical examination will include height, weight, and evaluation of general appearance, skin, eyes, ears, nose, throat, neck, lymph nodes, chest, heart, abdomen, and extremities.

e A brief neurological examination (mental status, cranial nerves, nystagmus, motor system, sensory system, reflexes, coordination, gait, and station) will be performed at all visits

f At-home doses will be recorded in the daily medication diary.

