g Following the Safety Period or if the patient withdraws early, the patient will enter a Taper Period. Patients will be tapered off of Cannabidiol Oral Solution as follows: 40 mg/kg/day will be reduced to 30mg/kg/day for five days, then 20 mg/kg/day for five days, then stop; 30 mg/kg/day for five days wil be reduced to 20 mg/kg/day for five days, then stop; 20 mg/kg/day can be discontinued without taper. This can be modified by the investigator based upon the patient's response.

h If the patient withdraws prematurely from the Safety Period, all Visit 7 (End of Study) procedures should be conducted. Site staff will follow up with the patient 4 weeks after completion of treatment via the telephone to collect information regarding AEs, AEDs, and concomitant medications.

i Follow-up Period visit (Visit 9) will be a phone call.

AE = adverse event; AED = anti-epileptic drug;

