**3.1.3. Follow-Up Period**

A follow-up telephone call (Visit 9) will occur 30 days after the Visit 7 (End of Study) or Early Withdrawal to assess AEs, AEDs, and record concomitant medications.

Approved

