## 7.2. End of Study (Visit 7) or Early Withdrawal

The following procedures and assessments will be performed:

- Review/assess past/current AEDs and concomitant medications.
- Record vital signs, collect blood samples for clinical labs, complete 12-lead ECG, and collect urine sample for urinalysis.
- Perform physical and brief neurological examinations.
- Collect/review CBD (dose may be modified up to 40 mg/kg/day at investigator's discretion).
- Perform drug accountability.
- Review AEs.
- Complete C-SSRS.
- Urine dipstick pregnancy test (all female patients of childbearing potential).
- Dispense CBD for Taper Period.
- End of Study assessments (If the patient withdraws prematurely from the Safety Period, all Visit 7 (End of Study) procedures should be conducted. Site staff will follow-up with the patient 4 weeks after completion of treatment via the telephone to collect information regarding AEs, AEDs, and concomitant medications.

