## 7.4. Follow-Up Period (Visit 9)

The following assessments will be performed by phone call 30 days after Visit 7 (End of Study) the last study dose:

- Review/assess past/current AEDs and concomitant medications.
- Review AEs.

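### The last adverse-event call (Visit 9) is dated from Visit 7 in some places and from the last dose in others; dated from Visit 7, drug-free follow-up is shortest after the highest final dose

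*Combined protocol and SAP*

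**What the plan says.** The protocol dates Visit 9, the last scheduled adverse-event (AE) enquiry, in several ways.

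- **From Visit 7 or Early Withdrawal.** Section 3.1, and the Synopsis Methodology in the same words: "A Follow-Up telephone call (Visit 9) will occur 30 days after the end of either the End of Study (Visit 7) or Early Withdrawal". Section 3.1.3: "A follow-up telephone call (Visit 9) will occur 30 days after the Visit 7 (End of Study) or Early Withdrawal". Table 1 has "30 Days After EOS" with a ±5-day window, and labels Visit 7 as End of Study.
- **From the end of drug.** Synopsis, Follow-Up Period: "A Follow-up telephone call will occur 30 days after discontinuation of the study drug".
- **From the end of treatment, early withdrawals only.** Table 1 footnote h: "Site staff will follow up with the patient 4 weeks after completion of treatment via the telephone". Section 7.2: "Site staff will follow-up with the patient 4 weeks after completion of treatment via the telephone".
- **Both at once.** Section 7.4: the assessments "will be performed by phone call 30 days after Visit 7 (End of Study) the last study dose".

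Section 3.1 also lists the periods in order: "The study will consist of a Safety Period (48±2 weeks), Taper Period (10±3 days), and a Follow-up Period (30±5 days". The Synopsis taper scheme and Section 3.1.2 start the taper the day after Visit 7. It takes two five-day steps from 40 mg/kg/day, one from 30, and none from 20 or below, and the investigator may modify it. The Synopsis puts the maximum time from Visit 1 to the follow-up call at about 54 weeks (±3 weeks).

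**The concern.** If the call is counted from Visit 7, the taper uses up part of the 30 days, and it uses most after the highest final dose. Time observed off drug then depends on dose. That is a systematic difference in ascertainment, unlike ordinary visit slippage.

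Safety and tolerability are the study's only objective, and AEs head the endpoint list in Section 8.1. Section 6.1.8.1 says when treatment-emergent monitoring begins. The protocol does not say on what day after the last dose an event stops counting as treatment-emergent, so the date of Visit 9 in practice sets the cut-off. Sites working from different sections would also call the same kind of patient on different days.

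**Working it through.** **Inputs.** Safety Period 48 weeks, Taper Period 10 days, Follow-up 30 days, with tolerances of 2 weeks, 3 days and 5 days (Section 3.1). Default taper of 10, 5 or 0 days, starting the day after Visit 7 (Section 3.1.2). Stated maximum about 54±3 weeks (Synopsis, Duration of treatment).

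**1. The plan's own duration.**
- Call after the taper: 48×7 + 10 + 30 = 376 days = 53.7 weeks, which rounds to 54.
- Call 30 days after Visit 7: 48×7 + 30 = 366 days = 52.3 weeks, which does not.
- The tolerance does not separate the two: 14+3+5 = 22 days = 3.1 weeks, against 14+5 = 19 days = 2.7 weeks. Both round to 3.

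**2. Drug-free days at the call.** On the Visit 7 anchor these are 30 − taper days. On the last-dose anchor they are always 30, and the call falls at taper days + 30.

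| Final dose (mg/kg/day) | Taper days | Drug-free days, Visit 7 anchor (±5) | Call day after Visit 7, last-dose anchor | Total weeks, last-dose anchor |
|---|---|---|---|---|
| 40 | 10 | 20 (15-25) | 40 | 53.7 |
| 30 | 5 | 25 (20-30) | 35 | 53.0 |
| ≤20 | 0 | 30 (25-35) | 30 | 52.3 |

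**3. Does the ±5-day window absorb the conflict?** After 40 mg/kg/day the windows are days 25-35 and days 35-45 after Visit 7, so they share a single day. For an early withdrawal from 40, with the taper starting the day after that visit, 4 weeks after treatment is day 10 + 28 = 38, outside days 25-35. From 30 it is day 33, inside. The gap between 28 and 30 days does not matter; the anchor does.

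**4. Size.** The final-dose mix is unknown. I assume 30 patients with the mix of the sponsor's earlier long-term study in Section 1.3 (91% above 20 mg/kg/day, 38% at 40), and take those in between as 30. That gives 11.4 patients at 40, 15.9 at 30 and 2.7 at ≤20.

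- Drug-free patient-days, Visit 7 anchor: 11.4×20 + 15.9×25 + 2.7×30 = 706.5.
- Last-dose anchor: 30×30 = 900. The loss is 193.5 days, or 21.5% of drug-free time. It ranges from 0% (all at ≤20) to 300/900 = 33% (all at 40).
- As a share of all observation from Visit 1: 30×366 = 10,980 days against 10,980 + 193.5 = 11,173.5, a loss of 1.7%.

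I also assume that new post-drug AEs start evenly over 30 days, with equal true incidence p at each dose. Expected patients missed = lost days × p/30.

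| p | Recorded at 40 (p×20/30) | Missed at 40 (114 lost days) | Missed at 30 (79.5 lost days) | Total |
|---|---|---|---|---|
| 5% | 3.3% | 0.19 | 0.13 | 0.32 |
| 10% | 6.7% | 0.38 | 0.27 | 0.65 |
| 20% | 13.3% | 0.76 | 0.53 | 1.29 |

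At p = 20% the total ranges from 0 (all at ≤20) to 300×0.20/30 = 2.0 patients (all at 40).

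**5. Is wash-out lost?** No. The longest mean half-life in Section 1.3 is 29.6 h, after a single dose. Five half-lives are 148 h = 6.2 days, well inside even 15 drug-free days.

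**The case against.** The best defence is that the intent can be recovered. The periods are listed in sequence, the 54-week figure works only if the call follows the taper, and the Synopsis Follow-Up Period, footnote h and Section 7.2 all count from the end of drug. That stands as evidence of intent. It does not settle the matter, because the Schedule of Events and Sections 3.1 and 3.1.3 say otherwise and nothing says which rule governs.

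The second defence is that little is lost, and that stands too. Section 7.3 reviews AEs in the taper. Section 6.1.8.8 follows serious and treatment-related AEs already known until they resolve or stabilise. Section 8.4.3 plans no inferential safety analysis.

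A reader might infer more than the documents support:

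- **That AE collection has no end.** Section 3.1.1 bounds it by the Follow-up Period, and Section 6.1.8.4 captures serious AEs to the end of the study. What the protocol lacks is one date for the end of follow-up and an explicit treatment-emergent cut-off. Section 8.4 leaves analysis detail to a SAP due before database lock.
- **That the AE tables will make 40 mg/kg/day look safer.** Those tables group by modal dose (Section 8.4.3.1), while taper length follows final dose. In a flexible-dose study the two can differ, so any such bias is only approximate.
- **That clobazam withdrawal effects are missed most at 40.** Section 1.3.2 gives a larger rise in clobazam exposure at 40 (×2.6) than at 20 (×1.5). Under the default taper, however, patients from 40 and 30 step down to 20 before stopping. The rest of the fall occurs in the taper, before Visit 9.
- **That the call must outlast the 4-week contraception requirement.** The call reviews only AEDs, concomitant medications and AEs (Section 7.4), and the requirement does not depend on its date.
- **That a 13-day taper could leave 12 drug-free days.** This relies on the ±3 days in Section 3.1. The default scheme takes at most 10 days.

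**Conclusion.** The conflict is real and should be resolved, but its effect is small. On the Visit 7 anchor, off-drug AE observation runs 20, 25 or 30 days after a final dose of 40, 30 or ≤20 mg/kg/day. What is at risk is detection of new-onset events on drug-free days 21-30 (from 40) or 26-30 (from 30).

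On the assumed dose mix, with incidence up to 20%, that is under one patient finishing on 40 mg/kg/day, and about 1.3 patients over both tapered groups at the 20% end. The dose mix, the even onset and the incidences are my assumptions. The 20, 25 and 30 days also require the default taper. For early withdrawals they require the taper to start the day after the Early Withdrawal visit; the Synopsis starts it after the patient's decision and Section 3.1.2 after the investigator is told.

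The point goes beyond wording, because the choice of anchor changes when the last scheduled safety enquiry takes place and whether off-drug observation is equal across final doses.

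**What to change.** Use one rule everywhere: *Visit 9 takes place 30±5 days after the last dose of CBD, taper included, for completers and early withdrawals alike.* Apply it in the Synopsis (Methodology and Follow-Up Period), Table 1 and its footnote h, and Sections 3.1, 3.1.3, 7.2 and 7.4. Define the treatment-emergent window as ending 30 days after the last dose.

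No visit or procedure is added. Compared with the Visit 7 anchor, the same phone call moves 10 days later after 40 mg/kg/day, 5 days later after 30, and not at all after ≤20. The stated duration already allows for this: with every upper tolerance used, 350 + 13 + 35 = 398 days = 56.9 weeks, within 54+3. The restrictions on other therapies in Section 4.7.2, which run through the Follow-up Period, would last correspondingly longer.
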